1.0 BACKGROUND AND RATIONALE

1.1 Background

Respiratory motion affects all tumor sites in the thorax and abdomen. The disease of most prevalence and relevance for motion-management needed radiotherapy are lung and liver cancer. Lung cancer is the leading cause of cancer-related mortality in the United States. During 2016, an estimated 224,390 new cases of lung cancer are diagnosed, representing 13% of all cancer patients¹, and an estimated 158,080 deaths of lung cancer were expected¹. The five-year survival rate for all stages combined is 17.7%, lower than many other leading cancer sites, such as the colon (64.4%), breast (89.7%) and prostate (98.9%)². Liver cancer is the 10th most common cancer. In 2016, an estimated 39,230 adults (28,410 men and 10,820 women) in the United States will be diagnosed with primary liver cancer¹. The 5-year survival rate of liver cancer is 17%².

Stereotactic body radiotherapy (SBRT) is a therapeutic paradigm developed in the mid 1990's. It administers very high, biological potent doses in few fractions (1 - 5 fractions) using unique beam arrangements and special immobilization equipment. It has demonstrated excellent local control in patients with inoperable non-small cell lung cancer (NSCLC)³ and liver cancer⁴.

Respiratory motion causes significant geometric and dosimetric uncertainties in lung and upper abdomen cancer radiotherapy treatment simulation, planning, and delivery⁵. These uncertainties are particularly large in SBRT, potentially leading to significant collateral toxicity⁶⁻⁸ when using large beam apertures or, conversely, potential marginal miss with very small apertures. Researchers and clinicians have been investigating respiratory motion-management techniques for over a decade.^{9, 10} A variety of motion management strategies have been explored and implemented for clinical use, including motion-encompassing methods [e.g. 4D CT and ITV (internal target volume) approach], abdominal compression techniques to decrease motion amplitude, breath-holding methods, respiratory-gating techniques, and real-time tumor-tracking methods. All of these techniques aim to mitigate dosimetric uncertainties induced by respiratory motion by either restricting or compensating for motion.

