4.3 Duration of Therapy

End of protocol therapy will be the last day of radiation. Other exceptions may apply:

- Disease progression
- Inter-current illness that prevents further administration of treatment
- Unacceptable adverse event(s)
- Subject decides to withdraw from the study, **OR**
- General or specific changes in the patient's condition render the subject unacceptable for further treatment in the judgment of the investigator".

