4.4 Duration of Follow Up

No follow-up required for this study after radiation completed.

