5.3 Follow-up procedures

- No follow-up required for this study after radiation completed. Follow-up per standard of care for SBRT treatment per treating radiation oncologist.

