7.0 ADVERSE EVENTS

7.1 Adverse Event Monitoring

Adverse event data collection and reporting, which are required as part of every clinical trial, are done to ensure the safety of subjects enrolled in the studies as well as those who will enroll in future studies. Adverse events are assessed in a routine manner at scheduled times during a trial. Additionally, certain adverse events must be reported in an expedited manner to allow for optimal monitoring of subject safety and care.

All subjects experiencing an adverse event, regardless of its relationship to study therapy, will be monitored until:

- the adverse event resolves or the symptoms or signs that constitute the adverse event return to baseline or is stable in the opinion of the investigator;
- there is a satisfactory explanation other than the study therapy for the changes observed; or
- death.

[Inserted from Adverse Event Definitions and Reporting Section – Appendix II of the SCCC DSMC Plan]

7.1.1 **Definitions**

An adverse event is defined as any untoward or unfavorable medical occurrence in a human research study participant, including any abnormal sign (for example, abnormal physical exam, imaging finding or clinically significant laboratory finding), symptom, clinical event, or disease, temporally associated with the subject's participation in the research, whether or not it is considered related to the subject's participation in the research.

Adverse events encompass clinical, physical and psychological harms. Adverse events occur most commonly in the context of biomedical research, although on occasion, they can occur in the context of social and behavioral research. Adverse events may be expected or unexpected.

Acute Adverse Events

Adverse events occurring in the time period from the signing of the informed consent, through **the last day of treatment** will be considered acute adverse events.

Severity

Adverse events will be graded by a numerical score according to the defined NCI Common Terminology Criteria for Adverse Events (NCI CTCAE) Version 5.0. Adverse events not specifically defined in the NCI CTCAE will be scored on the Adverse Event log according to the general guidelines provided by the NCI CTCAE and as outlined below.

- Grade 1: Mild
- Grade 2: Moderate
- Grade 3: Severe or medically significant but not immediately life threatening
- Grade 4: Life threatening consequences
- Grade 5: Death related to the adverse event

Serious Adverse Events

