7.1.2 Unanticipated Problems Involving Risks to Subjects or Others (UPIRSOs):

The phrase “unanticipated problems involving risks to subjects or others” is found, but not defined in the HHS regulations at 45 CFR 46, and the FDA regulations at 21 CFR 56.108(b)(1) and 21 CFR 312.66. For device studies, part 812 uses the term unanticipated adverse device effect, which is defined in 21 CFR 812.3(s). Guidance from the regulatory agencies considers unanticipated problems to include any incident, experience, or outcome that meets ALL three (3) of the following criteria:

- Unexpected in terms of nature, severity or frequency given (a) the research procedures that are described in the protocol-related documents, such as the IRB-approved research protocol and informed consent document; and (b) the characteristics of the subject population being studied;
AND
- Related or possibly related to participation in the research (possibly related means there is a reasonable possibility that the incident, experience, or outcome may have been caused by the procedures involved in the research);
AND
- Suggests that the research places subjects or others at greater risk of harm (including physical, psychological, economic, or social harm) than was previously known or recognized. Note: According to OHRP, if the adverse event is serious, it would always suggest a greater risk of harm.

Follow-up

All adverse events will be followed up according to good medical practices.

7.2 Steps to Determine If a Serious Adverse Event Requires Expedited Reporting to the SCCC DSMC

Step 1: Identify the type of adverse event using the NCI Common Terminology Criteria for Adverse Events (CTCAE v5).

Step 2: Grade the adverse event using the NCI CTCAE v5.

Step 3: Determine whether the adverse event is related to the protocol therapy.
Attribution categories are as follows:

- Definite – The AE is *clearly related* to the study treatment.

- Probable – The AE is *likely related* to the study treatment.
- Possible – The AE *may be related* to the study treatment.
- Unlikely – The AE *may NOT be related* to the study treatment.
- Unrelated – The AE is *clearly NOT related* to the study treatment.

Note: This includes all events that occur [to the end of the acute adverse events reporting period as defined in section 7.1.1.](#)

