Step 4: Determine the prior experience of the adverse event. Expected events are those that have been previously identified as resulting from administration of the treatment. An adverse event is considered unexpected, for expedited reporting purposes only, when either the type of event or the severity of the event is not listed in:

- the current known adverse events listed in the Agent Information Section of this protocol (if applicable);
- the drug package insert (if applicable);
- the current Investigator's Brochure (if applicable)
- the Study Agent(s)/Therapy(ies) Background and Associated Known Toxicities section of this protocol

7.2.1 Reporting SAEs and UPIRSOs to the Simmons Comprehensive Cancer Center (SCCC) Data Safety Monitoring Committee (DSMC)

SAEs and UPIRSOs at all sites, which occur in research subjects on protocols for which the SCCC is the DSMC of record require reporting to the DSMC regardless of whether IRB reporting is required. All SAEs occurring during the protocol-specified monitoring period and all UPIRSOs should be submitted to the SCCC DSMC within 5 business days of the study team members awareness of the event(s). In addition, for participating centers other than UTSW, local IRB guidance should be followed for local reporting of serious adverse events or unanticipated problems.

The UTSW study PI is responsible for ensuring SAEs/UPIRSOs are submitted to the SCCC DSMC Coordinator. This may be facilitated by the IIT project manager, study team, sub-site or other designee. Hardcopies or electronic versions of the eIRB Reportable Event report; FDA Form #3500A forms, or other sponsor forms, if applicable; and/or any other supporting documentation available should be submitted to the DSMC Coordinator. The DSMC Coordinator forwards the information onto the DSMC Chairman who determines if immediate action is required. Follow-up eIRB reports, and all subsequent SAE or UPIRSO documentation that is available are also submitted to the DSMC Chair who determines if further action is required. (See *Appendix III of the SCCC DSMC Plan for a template Serious Adverse Event Form which may be utilized*).

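### Adverse events that begin after the last fraction are not systematically collected or sent to the DSMC, and the rules for following open events are not reconciled with the absence of study follow-up

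*Combined protocol and SAP*

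**What the plan says.** All references are to the combined protocol and SAP.

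- **Onset window.** In 7.1.1, events from the signing of consent "through the last day of treatment will be considered acute adverse events". No post-treatment or late category follows. Section 4.3 fixes the closing date: "End of protocol therapy will be the last day of radiation".
- **Attribution.** The note to Step 3 in 7.2 covers events "to the end of the acute adverse events reporting period as defined in section 7.1.1".
- **Reporting to the DSMC.** Section 7.2.1 requires submission of "All SAEs occurring during the protocol-specified monitoring period", and also of all UPIRSOs, within 5 business days. The time restriction is attached to the SAEs only.
- **Follow-up.** Section 4.4: "No follow-up required for this study after radiation completed". Section 5.3 repeats this and adds: "Follow-up per standard of care for SBRT treatment per treating radiation oncologist".
- **Duty towards an event once it has occurred.** Section 7.1: "All subjects experiencing an adverse event, regardless of its relationship to study therapy, will be monitored until" it resolves, returns to baseline or is stable, has a satisfactory explanation other than study therapy, or the subject dies. Section 7.1.2 says that all adverse events are followed up, and 4.5 says that a subject removed from therapy is followed per protocol.
- **Schedule.** The Time and Events Table (5.4) has a pre-study and a treatment column, no post-treatment column and no adverse event row. Section 5.1.6 lists the screening adverse event assessment as none.

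**The concern.** Section 1.1 explains why motion management matters in SBRT: geometric and dosimetric uncertainty may lead to collateral toxicity or to a marginal miss. It describes SBRT as 1 to 5 fractions, so the treatment phase can be short. Toxicity of that kind need not begin before the last fraction, yet the study's collection of new events stops there. The physician also chooses the planning margin for each patient (5.2.2), while finding an adequate margin is a secondary objective (2.2.2 concerns the surface threshold, 2.2.1 the margin). Patients are thus treated before the study has answered that question.

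At stake is which safety events reach the DSMC, and whether staff know what to do with an event still open when radiation ends. Section 7.4 lists stopping rules as not applicable, so DSMC review of reported events is the main safety check.

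**Working it through.** **Step 1. Which window applies?** Section 7.2.1 refers to a monitoring period specified by the protocol. The only period the protocol defines is the acute one in 7.1.1, and the 7.2 note points to the same place. Collection by onset therefore runs from consent to the last day of radiation.

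**Step 2. What falls inside it?** The window opens at consent. It covers the oxygen-enhanced breath-hold training, the surface and tumor motion tests, simulation with the additional lower-dose CTs, and every fraction (4.1, 5.1.8, 5.2), as far as these follow consent. Harms that appear during these procedures are in scope.

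**Step 3. What happens to an SAE starting one day after the last fraction?**
- It is outside 7.1.1 and the 7.2 note, so no grading and attribution step applies.
- It is outside the SAE clause of 7.2.1.
- If it is a UPIRSO, it is reportable without a time limit. That requires an unexpected event in both definitions. Section 7.1.2 accepts a possible relation to the research, whereas the institutional definition under 7.2.1 requires a probable or definite one. Recognised SBRT toxicity would often not qualify as unexpected.
- If it is not a UPIRSO, 7.2.1 says that such events are tracked and summarised to the IRB at continuing review. It states no time limit and no way of collecting them after treatment.
- Detection depends on standard-of-care follow-up, which has no stated route into the study data.

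**Step 4. Can the follow-up rules be carried out?** An onset window in 7.1.1 and a follow-to-resolution rule in 7.1 are compatible: collect events that start in the window, then follow those. The difficulty lies elsewhere.

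| Duty | Provision for it |
|---|---|
| 7.1: monitor each event to an end state | 4.4 and 5.3: no study follow-up |
| 7.1.2: follow up all events | 5.4: no post-treatment column |
| 4.5: follow removed subjects per protocol | The protocol defines no such follow-up |
| 7.1: assess events at scheduled times | 5.4: no adverse event row |

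**Step 5. How much could be missed?** No figure in the plan bears on this, so there is none to reproduce. The sample of 10 (6.2) has no statistical derivation. As an illustration, let p be the probability that a patient has an event and f the share of such events that start inside the window. Both are assumptions. With 10 independent patients:

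P(at least one recorded) = 1 − (1 − p·f)^10

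For p = 0.10 and f = 0.25: 1 − 0.975^10 = 0.224.

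| p | f = 1 | f = 0.5 | f = 0.25 | f = 0.10 |
|---|---|---|---|---|
| 0.10 | 65% | 40% | 22% | 9.6% |
| 0.20 | 89% | 65% | 40% | 18% |
| 0.30 | 97% | 80% | 54% | 26% |

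For harms during breath-hold sessions f is near 1 and little is lost. For delayed harms f is low and the loss is large. Even with full capture, no events in 10 patients leaves a one-sided 95% upper bound of 1 − 0.05^(1/10) = 25.9%.

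**The case against.** The strongest case for the plan is that this is a ten-patient, single-arm pilot with no safety objective or endpoint. The procedures it adds all lie inside the window. The site already uses breath-hold with another device for lung and liver SBRT (1.2). The route from motion to harm is measured directly, through CBCT tumor position and recalculated dose to tumor and critical organs (5.2.8, 6.2, 6.3). Without a comparator, toxicity after treatment could hardly be attributed to surface monitoring rather than to the radiation itself. Unexpected related events remain reportable at any time. The timing of the first standard-of-care visit is not given, so the yield of a longer window is unknown.

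Much of this stands, and it rules out several stronger readings that a reader might infer:

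- *Almost no harm from the technique can be seen, or a single-fraction patient is observed only on the treatment day.* A single fraction shortens the treatment phase, not the window that opens at consent. The 1 to 5 fractions are a general description of SBRT; the study regimen is per standard of care.
- *The onset window contradicts the rule to monitor to resolution.* Step 4 shows that both can be obeyed.
- *Missing late events could make the technique look feasible.* Section 6.0 bases that judgment only on 50% of enrolled patients finishing breath-hold SBRT.

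The objection does not remove the core. Geometry and dose are not clinical events, the UPIRSO route is narrow, and the limited scope for attribution in 10 patients is a reason for cautious interpretation, not for leaving events uncollected.

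**Conclusion.** The point holds in limited form. Events with onset after the last fraction are not systematically collected, and SAEs among them have no stated route to the DSMC unless they are UPIRSOs. Scheduled study observation for new events after radiation is zero days. This reading assumes that the acute period in 7.1.1 is the monitoring period meant in 7.2.1, and the documents offer no other. Separately, the duties in 7.1, 7.1.2 and 4.5 have no mechanism in 4.4, 5.3 or 5.4.

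How many events would be lost cannot be derived from the documents; the table above is a range under assumed rates and onset shares. It would go too far to infer that a harmful technique would reach the DSMC as event-free: events up to the last fraction and all UPIRSOs are still reportable. The change is worth making because it is cheap and affects which safety events are reviewed.

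**What to change.** 1. In 7.1.1, the 7.2 note and 7.2.1, extend AE and SAE collection through the first standard-of-care follow-up visit after the last fraction, by chart review, and name this as the monitoring period.
2. Carry events still open at the last fraction to that visit and record their status.
3. In 5.4, add an adverse event row and a post-treatment column for the chart review.
4. Reword 4.4 and 5.3 to say that no study-specific visit is required but that this chart review takes place, and align 7.1, 7.1.2 and 4.5 with it. State what happens to an event that is still open at that visit.

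The cost is protocol wording and one chart review per patient, ten in total, or a few more if subjects are replaced under 4.6. No visit or procedure is added. Some unrelated or expected SBRT events will be recorded. Late effects would still not be captured, and because the timing of the visit is not stated, the protocol team should add it so that the length of the window is known.

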7.3 Unblinding Procedures

[Not applicable](#)

7.4 Stopping Rules

Not applicable

8.0 STUDY MANAGEMENT

8.1 Conflict of Interest

Any investigator who has a conflict of interest with this study (patent ownership, royalties, or financial gain greater than the minimum allowable by their institution, etc.) must have the conflict reviewed by the UTSW COI Committee and IRB according to UTSW Policy on Conflicts of Interest. All investigators will follow the University conflict of interest policy.

8.2 Institutional Review Board (IRB) Approval and Consent

It is expected that the IRB will have the proper representation and function in accordance with federally mandated regulations. The IRB must approve the consent form and protocol.

In obtaining and documenting informed consent, the investigator should comply with the applicable regulatory requirement(s), and should adhere to Good Clinical Practice (GCP) and to ethical principles that have their origin in the Declaration of Helsinki.

Before recruitment and enrollment onto this study, the subject will be given a full explanation of the study and will be given the opportunity to review the consent form. Each consent form must include all the relevant elements currently required by the FDA Regulations and local or state regulations. Once this essential information has been provided to the subject and the investigator is assured that the subject understands the implications of participating in the study, the subject will be asked to give consent to participate in the study by signing an IRB-approved consent form.

Prior to a patient's participation in the trial, the written informed consent form should be signed and personally dated by the subject and by the person who conducted the informed consent discussion.

8.3 Registration Procedures

All subjects must be registered with the Clinical Research Office, Department of Radiation Oncology, UTSW, before enrollment to study. Prior to registration, eligibility criteria must be confirmed with the Clinical research office Study Coordinator. To register a subject, call [contact] Monday through Friday, 9:00AM-5:00PM.

Each newly consented subject should be numbered using the schema provided above. Upon registration, the registrar will assign the additional registration/randomization code according to the numbering schema outlined

above, which should then be entered as the patient study id in Velos upon updating the status to enrolled.

The numbering schema should clearly identify the site number; the sequential number of the subject enrolled as well as the status of the subjects enrolled so that the number of subjects consented versus the number of subjects actually enrolled may be easily identified.

8.4 Data Management and Monitoring/Auditing

REDCap is the UTSW SCCC institutional choice for the electronic data capture of case report forms for SCCC Investigator Initiated Trials. REDCap will be used for electronic case report forms in accordance with Simmons Comprehensive Cancer Center requirements, as appropriate for the project

Trial monitoring will be conducted according to the study specific monitoring plan. For guidance on creating a monitoring plan, refer to the UTSW SCCC IIT Management Manual.

The UTSW Simmons Comprehensive Cancer Center (SCCC) Data Safety Monitoring Committee (DSMC) is responsible for monitoring data quality and patient safety for all UTSW SCCC clinical trials. As part of that responsibility, the DSMC reviews all serious adverse events and UPIRSOs in real time as they are reported and reviews adverse events on a quarterly basis. The quality assurance activity for the Clinical Research Office provides for periodic auditing of clinical research documents to ensure data integrity and regulatory compliance. A copy of the DSMC plan is available upon request.

The SCCC DSMC meets quarterly and conducts annual comprehensive reviews of ongoing clinical trials, for which it serves as the DSMC of record. The Quality Assurance Coordinator (QAC) works as part of the DSMC to conduct regular audits based on the level of risk. Audit findings are reviewed at the next available DSMC meeting. In this way, frequency of DSMC monitoring is dependent upon the level of risk. Risk level is determined by the DSMC Chairman and a number of factors such as the phase of the study; the type of investigational agent, device or intervention being studied; and monitoring required to ensure the safety of study subjects based on the associated risks of the study. Protocol-specific DSMC plans must be consistent with these principles.

8.5 Adherence to the Protocol

Except for an emergency situation, in which proper care for the protection, safety, and well-being of the study subject requires alternative treatment, the study shall be conducted exactly as described in the approved protocol.

8.5.1 Exceptions (also called single-subject exceptions or single-subject waivers): include any departure from IRB-approved research that is *not due to an emergency* and is:

- intentional on part of the investigator; or
- in the investigator's control; or
- not intended as a systemic change (e.g., single-subject exceptions to eligibility [inclusion/exclusion] criteria)

➤ **Reporting requirement***: Exceptions are non-emergency deviations that require **prospective** IRB approval before being implemented. Call the IRB if your request is urgent. If IRB approval is not obtained beforehand, this constitutes a major deviation. For eligibility waivers, studies which utilize the SCCC-DSMC as the DSMC of record must also obtain approval from the DSMC prior to submitting to IRB for approval.

8.5.2 Emergency Deviations: include any departure from IRB-approved research that is necessary to:

- avoid immediate apparent harm, or
- protect the life or physical well-being of subjects or others

➤ **Reporting requirement***: Emergency deviations must be promptly reported to the IRB within 5 working days of occurrence.

8.5.3 Serious Noncompliance (formerly called **major deviations or violations**): include any departure from IRB-approved research that:

- Increase risk of harm to subjects; and/or
- adversely affects the rights, safety, or welfare of subjects (any of which may also be an unanticipated problem); and/or
- adversely affects the integrity of the data and research (i.e., substantially compromises the integrity, reliability, or validity of the research)

➤ **Reporting requirement***: Serious Noncompliance must be promptly reported to the IRB within 5 working days of discovery..

8.5.4 Continuing Noncompliance: includes a pattern of repeated noncompliance (in or more protocols simultaneously, or over a period of time) which continues **after** initial discovery, including inadequate efforts to take or implement corrective or preventive action within a reasonable time frame.

➤ **Reporting requirement***: Continuing Noncompliance must be promptly reported to the IRB within 5 working days of discovery.

8.5.5 Noncompliance (that is neither serious nor continuing; formerly called minor deviations) any departure from IRB-approved research that:

- Does not meet the definition of serious noncompliance or continuing noncompliance

➤ **Reporting requirement***: Noncompliance that is neither serious nor continuing should be tracked and summarized the next IRB continuing review, or the notice of study closure- whichever comes first..

*Reporting Requirements reflect UTSW HRPP/IRB guidelines; participating sites should follow the reporting guidelines for their IRB of record

